13.2. Laboratory Evaluations

13.2.1. Clinical Laboratory Evaluations

The hematology laboratory analyses, clinical chemistry laboratory analyses, and urinalyses will be performed at a central laboratory. Reference ranges will be supplied by the central laboratory and used by the investigator to assess the laboratory data for clinical significance and pathological changes. Reference ranges will be provided in the laboratory manual.

The following parameters will be reported for laboratory data.

- **Hematology:** Hemoglobin, hematocrit, white blood cell (WBC) count (with differential including eosinophils), red blood cell (RBC) count, platelet count, and mean cell volume (MCV).
- **Chemistry:** Creatinine, aspartate aminotransferase (AST), alanine aminotransferase (ALT), gamma glutamyltransferase (GGT), alkaline phosphatase, lactate dehydrogenase (LDH), total bilirubin, direct bilirubin, creatinine phosphokinase ([CPK], CPK isoenzyme test will be performed only if CPK is

This document is confidential.

elevated to $> 2.5 \times \text{ULN}$), albumin, total protein, uric acid, sodium, potassium, calcium, chloride, glucose, urea, total cholesterol, triglycerides, low-density lipoprotein (LDL), and high-density lipoprotein (HDL). Follicle-stimulating hormone (FSH) will be collected for postmenopausal subjects.

- **Urinalysis:** pH, glucose, ketones, blood, protein, leukocytes, nitrites, bilirubin, urobilinogen, and specific gravity.

Laboratory assessments are performed at Screening, Baseline, Week 8, Week 16, Early Termination and Follow-up during the Initial Period.

Laboratory assessments are performed at Week 32, Week 48, Early Termination and Follow-Up during the Maintenance Period.

Hematology and chemistry laboratory data (absolute values and change from Baseline; and change from Week 16 for Maintenance Period) will be summarized as continuous variables (scheduled visits only) for the Initial Period and the Maintenance Period. Urinalysis laboratory data will be summarized by visit (scheduled visit only). Last post-baseline, worst post-baseline and maximum post-baseline results will also be included and will include unscheduled visits in the derivation. And worst post-baseline value will be defined as the highest or lowest value relative to the reference range during the respective treatment Period.

Shift tables will be generated using the reference ranges (Low, Normal, High and Missing) for hematology and chemistry laboratory data. The number and percentage of subjects shifting from reference ranges between Baseline and each visit (scheduled visits only) will be summarized for the Initial Period and the Maintenance Period. In addition, shift table from Week 16 will be provided for the Maintenance Period. Last, worst and maximum post baseline values will also be included in the shift tables and will include unscheduled visits in the derivation. Worst post baseline value will be defined as the highest or lowest value relative to the reference range.

Summary of the number and percentage of subjects who met criteria of potential clinically significant (CS) value will be summarized (scheduled visits only) for hematology and chemistry laboratory data. Last, worst and maximum post-baseline results will also be included in the summary. Potentially CS ranges for adult and adolescent are listed in sections 22.3 and 22.4.

For statistical and graphical summaries of the laboratory tests, values below or above the limit of detection (e.g. ' < 3 ' or ' >500 ') are substituted with the lower limit of detection minus 1% for values below the lower limit and are substituted with the upper limit of detection plus 1% for values above the upper limit (e.g. ' < 3 ' is substituted by ' 2.97 ', ' > 500 ' is substituted by ' 505 '). In data listings, the values are shown including the $<$ or $>$ sign.

Distribution of Aspartate Aminotransferase (AST), Alanine Aminotransferase (ALT), Alkaline Phosphatase (ALP), Total bilirubin and Creatinine Phosphokinase (CPK) will be displayed graphically as boxplot by treatment group for each scheduled visit and the maximum post-Baseline (including unscheduled visits in the derivation) values for the Initial Period and the Maintenance Period.

By-subject listing will be presented for all laboratory data. By-subject listing for subjects with at least one abnormal result (out of reference range) will be provided for hematology and clinical chemistry. By-subject listing for subjects with at least one potentially CS result will be provided for hematology and clinical chemistry.

This document is confidential.

All laboratory data will be listed for the Safety population.

13.2.2. Pregnancy Testing

All women of childbearing potential will have a serum pregnancy test at the screening visit and urine pregnancy tests (UPTs) at Baseline, Week 4, Week 8, Week 12 and Week 16, Early termination visit, and Follow-up of the Initial Period. UPTs will also be performed at Week 20, Week 24, Week 28, Week 32, Week 36, Week 40, Week 44, and Week 48, Early termination visit, and Follow-up of the Maintenance Period. Pregnancy test results must be available prior to the administration of the study drug.

All confirmed pregnancy test results, premenses status and childbearing potential assessment results will be listed on the Safety population.

13.2.3. Virology and TB Testing

Virology including HBsAg, HBcAb, hepatitis C, HIV-1, and HIV-2 antibody will be assessed at the screening visit. Subjects with a positive HBcAb and a negative HBsAg will also be assessed for hepatitis B surface antibody.

All virology results will be listed on the Safety population.

Subjects will be assessed for TB infection with a QuantiFERON-TB Gold test at the screening visit.

All TB test results will be listed on the Safety population.

13.3. Vital Signs

Vital signs will include pulse rate, systolic and diastolic blood pressure (after the subject has been sitting for at least 5 minutes) and body temperature.

Vital signs will be collected at the Screening visit and at Baseline, Week 4, Week 8, Week 12 and Week 16, Early termination visit, and at Follow-up of the Initial Period. Vital signs will also be collected at Week 20, Week 24, Week 28, Week 32, Week 36, Week 40, Week 44, Week 48, Early termination visit, and at Follow-up of the Maintenance Period.

Height and weight will be measured at Screening for all subjects. Height assessments will be conducted for adolescent subjects (aged 12-17) at Week 8 and 16 of the Initial Period, as well as Week 24, Week 32, Week 40, and Week 48 of the Maintenance Period and at Follow-up. Weight assessments will be conducted for adolescent subjects at Baseline, and Week 16 of the Initial Period as well as at Week 32, and Week 48 of the Maintenance Period and at Follow-up.

All vital signs including height and weight (absolute values and change from Baseline; and change from Week 16 for Maintenance Period) will be summarized as continuous (scheduled visits only) for the Initial Period and the Maintenance Period. Last post-Baseline results (including unscheduled visits in the derivation) will also be included.

The number and percentage of subjects who met criteria of potential CS value for vital signs and weight will be summarized (scheduled visits only) for the Initial Period and the Maintenance Period. Last post-Baseline results (including unscheduled visits in the derivation) will also be included.

This document is confidential.

Distribution of pulse rate, systolic and diastolic blood pressure will be displayed graphically as boxplot by treatment group for each scheduled visit and maximum post-Baseline (including unscheduled visits in the derivation) values for the Initial Period and the Maintenance Period.

By-subject listing of subjects with potentially CS vital signs and weight will be provided.

Potentially CS ranges for adult and adolescent are in sections 22.3 and 22.4.

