#### **10.1.4.4 Vital Signs**

All vital signs and weight data (absolute values and change from baseline) will be summarized by visit and treatment group. In addition, the number and percent of subjects with clinically significant abnormal values (of clinical concern as identified by the investigator) will be summarized by treatment group.

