8.1. General Methods

All data will be listed, and summary tables will be provided. Summaries will be presented for each treatment and visit (if applicable).

Unless otherwise stated, continuous variables will be summarized using the number of observations (n), mean, standard deviation (SD), median, Q1, Q3, minimum, and maximum by treatment group and visit (if applicable). Categorical variables will be summarized using frequency and percentages of subjects for each category by treatment group and visit (if applicable).

Unless otherwise stated, all statistical tests will be 2-sided and conducted at the 5% level; all presented confidence intervals (CIs) will be 2-sided 95% CIs.

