In case of missing/skipped visit, unscheduled or early termination visit, the diary data will be windowed based on the study day (see Tables 8-3 and 8-4). If a subject missed/skipped a visit due to any reason (e.g., skipped a visit due to COVID-19), the diary data which have been reported during that time will be mapped to the analysis visit based on the study day and 7 days consecutive data will be classified into the analysis visit as in the tables below. For the unscheduled or early termination visit data, the same approach will be applied to window the data into analysis visit.

CCI [Redacted]

Table 8-3: Analysis Visit Window for Missing/Skipped Visit, Unscheduled or Early termination Visit for PP/CCI [Redacted] NRS and CCI [Redacted]

Analysis Visit	Target Study Day of Analysis Visit	Visit Window for evening assessment (PP NRS, CCI [Redacted])*
Week 24	169	162 to 168
Week 32	225	218 to 224
Week 40	281	274 to 280
Week 48	337	330 to 336

CCI [Redacted]

* for evening diary, only the data before dosing on the clinic visit date will be considered for analysis.

CCI [Redacted]

Approved 10-Nov-2022 00:00:00

This document is confidential.

* if <4 days non-missing data within Week 16 window, the upper bound will be extended first up to +5 days to obtain 4 non-missing data. If still <4 non-missing data after extending the upper bound, the lower bound will be extended again up to +5 days to obtain 4 days non-missing data. Only the data before Week 16 dosing (or re-randomization if missing Week 16 dosing) will be considered for Initial Treatment Period analysis.

For efficacy, where two or more assessments (including both scheduled and unscheduled assessments) are available for the same visit interval, the one closest to the target visit date will be used for the summary and analyses. Safety and CCI data will not be windowed for by-visit summary. i.e., scheduled visit data will be used for analysis.

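### The table of potentially clinically significant vital signs and weight has no worst or any-post-baseline row, so a transient reading at an unscheduled visit enters no count by arm

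*SAP*

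**What the plan says.** SAP 13.3 (Vital Signs) plans four outputs that bear on PCS values:

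- **PCS count.** A count with its percentage in each of the two treatment periods. It covers those "who met criteria of potential CS value for vital signs and weight will be summarized (scheduled visits only").
- **Last-value row.** "Last post-Baseline results (including unscheduled visits in the derivation) will also be included".
- **Boxplots.** Pulse, systolic and diastolic pressure, split by arm. They show "each scheduled visit and maximum post-Baseline (including unscheduled visits in the derivation) values for the Initial Period and the Maintenance Period".
- **Listing.** "By-subject listing of subjects with potentially CS vital signs and weight will be provided". No limit to scheduled visits is stated.

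For the corresponding laboratory PCS table, SAP 13.2.1 says: "Last, worst and maximum post-baseline results will also be included in the summary". That sentence does not itself mention unscheduled visits, but the paragraphs of the same section on the summary and shift tables bring them into the derivation of the last, worst and maximum values.

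Two general rules affect the layout. SAP 8.1: "Summaries will be presented for each treatment and visit (if applicable"). SAP 8.4, on by-visit summaries of safety data: "scheduled visit data will be used for analysis".

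Protocol 10.1.4.4 plans a related but different output: a tally by arm of subjects whose abnormal vital signs the investigator considers clinically significant. It has no visit restriction, but it rests on investigator judgement, whereas the SAP applies the numeric ranges of its Sections 22.3 and 22.4.

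**The concern.** A PCS table exists to show how many subjects in each arm crossed a preset threshold at any time on treatment. A count confined to scheduled visits leaves out readings taken when something prompted an extra visit. Protocol 8.5.2 names adverse event follow-up as one purpose of unscheduled visits, and the schedule of assessments allows vital signs at them. An abnormal pulse or pressure recorded there, and normal again by the last assessment, is not counted.

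There is a second gap if the table has one row per visit. Subjects flagged at different visits then fall in different rows, and the rows cannot be added because one subject may appear in several. The reader could not recover an incidence by arm from the table. The listing would show the cases but no rate, and under 2:1 randomization raw case counts in the Initial Period are not directly comparable between arms.

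At stake is the completeness of one descriptive safety table. No hypothesis test or stopping rule is attached to it in the SAP.

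**Working it through.** The documents give no figure on this point, so there is none to reproduce. The check has two parts: where a reading can appear, and how far a by-visit row can differ from an any-time count.

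**1. Tracing one reading.** Take a PCS reading at an unscheduled visit that is not the subject's last post-baseline value.

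| Output | Does the reading appear? |
|---|---|
| PCS count, scheduled visits | No |
| PCS last-value row | No; only if it were the last value |
| Maximum boxplots | Only if it is that subject's maximum pulse or blood pressure. No low values, no weight, and the PCS criteria are not applied |
| By-subject PCS listing | Yes, on the wording; no rate by arm |
| Adverse event tables (SAP 13.1) | Only if judged a clinically significant change from screening (Protocol 9.2.6) |

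The boxplots are a partial substitute at best. The adult criteria in SAP 22.3 include low limits combined with a change from baseline (for example pulse at or below 50 bpm with a fall of at least 20 bpm) and a weight change of 5% in either direction.

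**2. By visit or by period.** The PCS sentence does not say by visit. SAP 8.1, SAP 8.4 and the addition of a last-value row make that layout likely. Only table titles are available, so it cannot be confirmed.

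- If by visit: no row counts subjects who ever met a criterion.
- If one count per period over scheduled visits: that gap closes, but the unscheduled reading in part 1 is still excluded.

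**3. Size on the by-visit layout, scheduled readings only.** Inputs from the schedule of assessments and SAP 13.3, on-treatment post-baseline visits:

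- Pulse and blood pressure: Initial Period k = 4 (Weeks 4, 8, 12, 16); Maintenance Period k = 8 (Weeks 20, 24, 28, 32, 36, 40, 44, 48).
- Weight: Initial Period k = 1 (Week 16); Maintenance Period k = 2 (Weeks 32, 48).

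Let p be the proportion meeting a criterion at each visit. It is not in the documents and is assumed equal across visits. Without any independence assumption, the any-time proportion lies between p (the same subjects at every visit) and k × p (different subjects at every visit). The ratio of the any-time proportion to a printed row is therefore between 1 and k. With independent visits it is 1 − (1 − p)^k.

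For pulse and blood pressure:

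| Assumed p | Initial, k = 4: range (independent) | Maintenance, k = 8: range (independent) |
|---|---|---|
| 0.5% | 0.5% to 2% (2.0%) | 0.5% to 4% (3.9%) |
| 1% | 1% to 4% (3.9%) | 1% to 8% (7.7%) |
| 2% | 2% to 8% (7.8%) | 2% to 16% (14.9%) |
| 5% | 5% to 20% (18.6%) | 5% to 40% (33.7%) |

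For example, at p = 1%: 1 − 0.99^4 = 3.9% and 1 − 0.99^8 = 7.7%.

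For weight the ratio is exactly 1 in the Initial Period (k = 1) and between 1 and 2 in the Maintenance Period (k = 2). Unscheduled readings would come on top and cannot be bounded from the documents.

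**The case against.** The strongest reply is that little is lost. Unscheduled readings reach the last-value row when they are last, the maximum boxplots by arm, and the PCS listing. Protocol 9.2.6 has clinically significant changes in vital signs recorded as adverse events, and these are tabulated as subject-level percentages by arm and period without restriction to scheduled visits. What is missing is only an any-time count against numeric thresholds, including readings that the investigator judged unimportant. All of this stands, and it keeps the point small.

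A second reply is that the laboratory rule does not carry over directly. SAP 13.2.1 defines worst relative to the reference range, and SAP 22.3 and 22.4 give no reference range for vital signs or weight. This also stands. It argues for an any-post-baseline row and not a worst row; it is not a reason to have neither.

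Four stronger readings might be inferred, and the documents do not support them:

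- *Unscheduled readings are lost.* They can be absent from the count, but other outputs can show them.
- *No subject-level incidence is tabulated at all.* This depends on an inferred by-visit layout and overlooks the adverse event tables.
- *Incidence is understated 4-fold or 8-fold.* These are upper limits for pulse and blood pressure only. They need nearly every flag to fall on a different subject, and they do not apply to weight.
- *The SAP contradicts Protocol 10.1.4.4.* That count is investigator-judged and the SAP's is threshold-based. They are different outputs, although SAP Section 15 does not mention the change.

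**Conclusion.** The concern holds in a limited form. As written, SAP 13.3 leaves a transient PCS reading at an unscheduled visit out of every PCS count by arm unless it is the last value, whichever layout is used. The laboratory PCS table in the same SAP has worst and maximum rows, and no reason is given for the difference.

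That the table also lacks a count of subjects who ever met a criterion rests on the by-visit layout, which is likely but not stated. On that layout the understatement from scheduled readings alone could be nil. Its ceiling is about 4-fold (Initial Period) and 8-fold (Maintenance Period) for pulse and blood pressure; for weight it is none and at most 2-fold. These ceilings assume the same rate at each visit. The documents do not show where in the range the truth lies, or how many unscheduled readings there will be.

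This is a worthwhile, nearly free improvement to safety reporting. It does not affect the efficacy analyses or trial conduct.

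**What to change.** Add to SAP 13.3, and to Tables 14.3.4.2.3 (Initial Period) and 14.3.4.2.4 (Maintenance Period), a rule such as: for each criterion, present by treatment group the number and percentage of subjects with at least one PCS value at any post-baseline assessment in the period, including unscheduled visits, with low and high criteria shown separately.

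The same paragraph should say whether the existing scheduled-visit count is given by visit or once per period.

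The cost is one or two sentences in the SAP and one row per criterion in two tables. No new data are needed: the SAP already flags PCS values for the listing and already draws on unscheduled visits for the last-value rows and the maximum boxplots.

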13.4. ECG

A 12-lead Electrocardiogram (ECG) will be performed and read centrally at Screening, Week 16, Week 48, Early termination visit, and at Follow-up.

The overall results of the ECGs recorded as 'Normal', 'Abnormal, NCS' or 'Abnormal, CS' will be summarized by treatment group and visit (scheduled visits only) for the Initial Period and the Maintenance Period. Clinical significance will be determined by the investigator.

13.5. Physical Examination

A complete physical examination will include assessments of the head, ears, eyes, nose, throat, neck (including thyroid), skin/integumentary system, cardiovascular system, respiratory system, gastrointestinal system, musculoskeletal system, lymph nodes, nervous system, and extremities.

A physical examination will be performed at Screening, Baseline, Week 4, Week 8, and Week 16 of the Initial Period. Physical examination will also be performed at Week 24, Week 32, Week 40, and Week 48 of the Maintenance Period, as well as at Early termination visit, and at Follow-up.

The number and percentage of subjects with physical examination results classified as 'Normal', 'Abnormal, not Clinically Significant (NCS)' or 'Abnormal, CS' will be summarized (scheduled visits only), and body system for the Initial Period and the Maintenance Period.

Shift from Baseline of the physical examination category will also be summarized by body system for the Initial Treatment Period and shift from Baseline and from Week 16 will be summarized for the Maintenance Period.

By-subject listing will be provided for subjects who have at least one abnormal results from any body system or who missed the assessment due to any reason.

13.6. Respiratory Assessments

13.6.1. Respiratory Examination and PEF Testing

A respiratory examination consisting of questions regarding medical history of asthma, wheeze, dyspnea, and cough, will be performed for all subjects at Screening, Baseline, Week 4, Week 8, Week 12 and Week 16 of the Initial Period and at Week 20, Week 24, Week 28, Week 32, Week 36, Week 40, Week 44, and Week 48 of the Maintenance Period, as well as at Early termination visit, and at Follow-up.

Respiratory examination questionnaire results will be listed on the Safety population.

PEF testing will be performed for all subjects at Screening, Baseline, Week 4, Week 8, Week 12 and Week 16 of the Initial Period and at Week 20, Week 24, Week 28, Week 32, Week 36, Week 40, Week 44, and Week 48 of the Maintenance Period, as well as at Early termination visit, and at Follow-up.

This document is confidential.

PEF (absolute values and change from Baseline; and change from Week 16 for the Maintenance Period) will be summarized as a continuous variable (scheduled visits only) for the Initial Period and the Maintenance Period. PEF will be summarized separately for the subset of subjects with, and without, a history of asthma.

The number and percentage of subjects with PEF < 80% will be summarized by treatment group, visit (scheduled visits only), and medical history of asthma (with and without history of asthma) for the Initial Treatment Period and the Maintenance Period.

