j Pruritus assessments (ie, PP NRS, CCI) will be recorded the evening before the clinic visit. If a subject does not complete the CCI in the evening before a scheduled visit, the subject will be allowed to complete the assessment the following day at the clinic visit before investigator assessments, laboratory sample collection, and study drug administration. See Sections: 9.7.4, 9.7.5, and 9.7.6

k Assessments to be completed by subjects for 7 consecutive days before the designated target visit dates during study treatment.

l Optional photographs of AD lesions will be performed only for consenting subjects at selected sites. See Section 9.8 for details.

CONFIDENTIAL

Galderma S.A./Galderma R&D, LLC

4 Nov 2021

Protocol Number: RD.06.SPR.118169

Version 8.0

Page 58 of 186

- m Subjects with a history of asthma will complete the ACT (and PEF testing) at each scheduled visit. Subjects with de novo asthma will complete the ACT (and PEF testing) beginning from de novo diagnosis and at all subsequent scheduled visits. See Section 9.2.9.1 for details.
- n At screening, the investigator should specifically question all subjects about any medical history of asthma and their respiratory health (eg, wheezing, coughing, allergies, infections). A respiratory examination will be required for all subjects at all scheduled visits. See Section 9.2.9.2 for details.
- o PEF testing will be performed for all subjects at screening, baseline, Week 8, 16, 32, 48, and follow up visits. For subjects reporting a medical history of asthma, PEF testing (and ACT) will be performed at all visits during the clinical study. For subjects diagnosed with de novo asthma, PEF testing (and ACT) will be performed at all visits, starting with the visit in which the diagnosis was confirmed. Subjects should be asked to withhold asthma medication on study visit days until after PEF testing is complete, to the extent it does not pose an undue risk to the subject. See Section 9.2.9.3 for details.
- p Complete PE should be performed at designated visits. See Section 9.2.8 for PE details.
- q Contraceptive counseling should occur at screening or at applicable visits when pre-pubertal subjects begin menses.
- r Height collection will be performed for all subjects at screening. Height collection is only required for adolescents (ages 12-17) at designated post-screening visits.

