### 8.5.2 Unscheduled Visit

The subject should be reminded to adhere to the study schedule. Unscheduled visits are defined as visits to repeat testing for abnormal laboratory results, for follow-up of AEs, or to conduct efficacy assessments for subjects requiring rescue medication between regularly scheduled study visits. Visits occurring outside of the visit window are not considered unscheduled visits.

Assessments to be conducted at the unscheduled visit will depend on the reason for the visit: Any of the procedures/assessments listed in Section 8.1.2 may be conducted, but not all are required. Blood sample collection for PK and ADA analyses are only required during unscheduled visits that are conducted for safety reasons.

CONFIDENTIAL

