13.6.2. Asthma Control Test

Subjects with a medical history of asthma will take an Asthma Control Test (ACT) at Screening, Baseline, Week 4, Week 8, Week 12 and Week 16 of the Initial Period and at Week 20, Week 24, Week 28, Week 32, Week 36, Week 40, Week 44, and Week 48 of the Maintenance Period, as well as at Early termination visit, and Follow-up.

[figure not shown]
The ACT is designed for adults and adolescents 12 years or older, and is composed of 5 questions. For each question, the subject will choose the best answer out of 5 possible answers. The test provides a numerical score ranging from 5 to 25 to assess asthma control; a higher score indicates better asthma control while a score of 19 or less indicates the subject's asthma may not be under control.

Subjects with a new (de novo) diagnosis of asthma during the trial will take the ACT beginning at the visit the diagnosis was first confirmed and at all subsequent study visits thereafter.

ACT total score (absolute values and change from Baseline) will be summarized as a continuous variable (scheduled visits only) for the Initial Treatment Period and the Maintenance Period.

The number and percentage of subjects with an ACT score \leq 19 will be summarized (scheduled visits only) for the Initial Period and the Maintenance Period.

CCI

This document is confidential.

14. Interim Analyses

No interim analysis is planned.

1.0

CD14152.SPR118169.SAP.V01

Approved 10-Nov-2022 00:00:00

This document is confidential.

15. Changes from Analysis Planned in Protocol

In protocol Section 8.4.9 (Prior and Concomitant Therapies), concomitant medications/therapies are defined as any therapies taken during the study (i.e., from the screening visit to the end of study).

However, for the analysis purpose, concomitant medications/therapies are defined as medications/therapies which start or stop or ongoing on or after the 1st injection of study drug.

1.0

CD14152.SPR118169.SAP.V01

Approved 10-Nov-2022 00:00:00

This document is confidential.

16. Reference List

Not applicable.

1.0

CD14152.SPR118169.SAP.V01

Approved 10-Nov-2022 00:00:00

This document is confidential.

17. Programming Considerations

All TFLs and statistical analyses will be generated using SAS® 9.4 or higher (SAS® Institute Inc., Cary, NC, USA). Computer-generated TFL output will adhere to the following specifications.

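### The PEF <80% and ACT ≤19 tables count scheduled visits only and give no per-subject ever-low count or worst value, unlike the laboratory tables

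*SAP*

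**What the plan says.** SAP 13.6.1: the number and percentage of subjects with PEF below 80% "will be summarized by treatment group, visit (scheduled visits only), and medical history of asthma". SAP 13.6.2: the number and percentage with ACT ≤19 "will be summarized (scheduled visits only) for the Initial Period and the Maintenance Period". The continuous PEF and ACT summaries carry the same limit. SAP 8.4 gives the general rule: safety data "will not be windowed for by-visit summary. i.e., scheduled visit data will be used for analysis".

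For laboratory data, SAP 13.2.1 adds further rows: "Last post-baseline, worst post-baseline and maximum post-baseline results will also be included and will include unscheduled visits in the derivation". For vital signs, SAP 13.3 adds one: "Last post-Baseline results (including unscheduled visits in the derivation) will also be included". Nothing equivalent appears for PEF or ACT in SAP 13.6 or in the titles of tables 14.3.4.4.6 to 14.3.4.4.15.

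Protocol 8.5.2 describes what unscheduled visits are for: "Unscheduled visits are defined as visits to repeat testing for abnormal laboratory results, for follow-up of AEs", as well as efficacy assessments before rescue. On content it says: "Any of the procedures/assessments listed in Section 8.1.2 may be conducted, but not all are required". The schedule of assessments marks PEF and ACT in the unscheduled-visit column, in parentheses.

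**The concern.** Phase 2b showed a dose-dependent rise in asthma flares among subjects with pre-existing asthma: 1 (1.8%) on placebo against 7 (12.3%) on 30 mg (protocol 6.2.3). PEF and ACT are the objective measures this trial collects on that risk. Two features weaken their tables.

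- **Unscheduled values have no place.** A subject brought back because of a respiratory complaint may have a low PEF recorded at that visit and be normal at the next fixed visit. The threshold table then shows no low value for that subject.
- **By-visit rows do not give an incidence.** They show how many subjects were low at each visit, not how many were ever low, even when every value came from a scheduled visit.

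The PEF and ACT tables offer a check on event reporting that does not depend on whether an investigator judged a value reportable. Leaving out values from AE follow-up visits removes part of that check.

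**Working it through.** The plan states no figure on this point, so the check is a comparison of passages, with one bound.

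**1. Which values reach a summary row**

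| Data | By-visit rows | Added post-baseline rows | Unscheduled values in the added rows |
|---|---|---|---|
| Laboratory (SAP 13.2.1) | scheduled only | last, worst, maximum | yes |
| Vital signs (SAP 13.3) | scheduled only | last (maximum in boxplots) | yes |
| PEF (SAP 13.6.1) | scheduled only | none | not applicable |
| ACT (SAP 13.6.2) | scheduled only | none | not applicable |

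The laboratory shift tables and potentially clinically significant summaries also carry last, worst and maximum rows.

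**2. Can unscheduled PEF or ACT values exist?** Yes, but they are optional under protocol 8.5.2. Protocol Appendix 2 also plans a remote unscheduled safety visit before a delayed Week 16 visit, and lists PEF and ACT among the assessments to be collected remotely.

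**3. Is an ever-low count an incidence?** Essentially yes. Exclusion criteria 2c and 2d bar PEF below 80% of predicted at screening or baseline, and ACT ≤19 in subjects with a history of asthma. Apart from eligibility deviations, a later low value is new.

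**4. What by-visit rows leave open.** If a proportion p of the same subjects is low at each of k visits, the ever-low proportion lies between p (the same subjects each time) and the smaller of 1 and k × p (different subjects each time). Take p = 3%, which is assumed for illustration:

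- Asthma history, initial period, k = 4 (Weeks 4, 8, 12, 16): 3% to 4 × 3% = 12%.
- No asthma history, initial period, k = 2 (Weeks 8 and 16, using the schedule footnote): 3% to 2 × 3% = 6%.

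**5. Other routes to a table for a low unscheduled value** (protocol 9.2.1.1)

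- PEF <80% with an asthma history: an AESI should be reported.
- ACT ≤19 with an asthma history: an AESI is reported on investigator judgment, taking account of the managing physician's report.
- PEF decline without an asthma history: an AESI is reported on investigator judgment of the specialist's report. There is one exception: Appendix 2 asks for an AESI when a remotely measured PEF stays below 80%, whatever the history.

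**6. Listings.** Listings 16.2.8.2.5 (PEF) and 16.2.8.2.7 (ACT) state no scheduled-visit limit. Listing 16.2.8.2.8 uses a different criterion, a fall of at least 15% from baseline. A subject going from 82% to 78% of predicted, with the predicted value unchanged, falls by (82 − 78)/82 = 4.9%. That subject crosses the 80% line but is not in this listing. Listings also give no comparison by arm.

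**7. Denominators.** SAP 13.6.1 has PEF done for all subjects at every visit. The schedule footnote says: "PEF testing will be performed for all subjects at screening, baseline, Week 8, 16, 32, 48, and follow up visits", with the other visits only for subjects with a history of asthma or a new diagnosis. The SAP's own Table 4-3 repeats the footnote, so the SAP conflicts with itself as well as with the protocol.

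**8. Size.** The undercount depends on how many unscheduled PEF and ACT measurements occur and how many are low with no low value at a scheduled visit in the same period. The documents give neither number.

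**The case against.** The strongest reply is that the asthma risk is tabulated through events, and those tables have no scheduled-visit limit. New or worsening asthma is an AESI. TEAEs run from first dose to the end of study. The adjudication committee reviews every asthma-related AE, and SAP 13.1 plans adjudicated tables and tables setting investigator reports beside the committee's outcome. Each subject counts once for a given AE, so a per-subject incidence of reported asthma events already exists. This stands. A reader might infer that the asthma signal is missing from the safety tables; the documents do not support that. What remains are ACT values, and PEF values without an asthma history, that the investigator judges not to be an AESI, together with the absence of any ever-low count.

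A second reply is that scheduled-only rows are the SAP's general convention, also used for ECG and physical examination, and give both arms equal opportunity for measurement, whereas unscheduled testing is driven by symptoms. This also stands. It is a reason to keep the by-visit rows and to show counts both ways. It does not explain why laboratory data get a worst-value row and PEF and ACT do not.

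A reader might also try to size the loss by dividing an assumed episode length by the interval between visits. That measures how often a fixed visit lands inside an episode, which is a property of visit spacing. An added row recovers an episode only if an unscheduled visit took place and PEF or ACT was done there.

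**Conclusion.** The point holds for the PEF and ACT value tables. They omit unscheduled values and provide neither an ever-low count nor a worst value, although the SAP already does better for laboratory data. A low value seen only at an unscheduled visit reaches a table only through AE or AESI reporting, which is partly a matter of judgment. The missing incidence measure does not depend on how many unscheduled visits occur; the loss of unscheduled values does, and it cannot be sized from the documents.

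Two further inferences should be avoided. Calling asthma the main safety risk goes beyond protocol 6.2.3, which names it together with infections, although asthma has its own adjudication committee. Nor do the documents show that the arm comparison is distorted in a known direction: if the same share of cases is missed in both arms, the absolute difference shrinks but the ratio is unchanged.

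This is an inexpensive improvement that should be made. It is not a flaw that undermines the safety evaluation.

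**What to change.** In SAP 13.6.1 and 13.6.2, keep the by-visit rows and add, by period, arm and asthma history:

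- the number and percentage of subjects with any post-baseline PEF below 80% of predicted, and with any post-baseline ACT ≤19, shown (a) for scheduled visits only and (b) including unscheduled and early termination visits;
- the worst (lowest) post-baseline PEF and ACT, using the derivation already written for laboratory data.

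Assign unscheduled values to a period by date, using the definitions in SAP 8.2, and state the denominator as subjects with at least one post-baseline measurement. Read (b) beside (a), because unscheduled testing follows symptoms. ACT in subjects without an asthma history arises only after a new diagnosis, so its denominator needs a footnote.

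Separately, reconcile SAP 13.6.1 with the schedule footnotes in protocol 8.1.2 and SAP Table 4-3 on which subjects have PEF at which visits.

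The cost is SAP wording and a few rows in tables 14.3.4.4.6 to 14.3.4.4.15. No new data collection is needed.
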